Using this approach, it is expected to address the informatics challenge of determining how to design information technology that improves engagement and clinical outcomes for patients who require continuous monitoring and who engage an informal caregiver in self-management outside clinical settings. Our work extends the design of remote-monitoring systems from stationary, home-based systems to wearable devices that patients can engage with throughout an active day in the community. Our research team—which consists in a biomedical systems engineer, a human factors engineer specialized in consumer health informatics, a pediatric endocrinologist, and a pediatrician specialized in clinical research — works in alliance with the Center for Diabetes Technology at the University of Virginia. Study team members have developed this ambulatory platform that will be used as the foundation for this study.

Rationale: The hypothesis of this study is that individuals randomized to the CGM/Fitbit with no weekly feedback (Control Group) will improve management modestly initially (as a result of either of new access to CGM or the Hawthorne effect of being studied), but their measures of engagement (patient self-management behavior (i.e. personal insulin parameters) and diabetes-related dyad communication) will return to baseline levels by the 12-week evaluation. By contrast, it is hypothesize that individuals randomized to CloudConnect (Experimental Group) will have a greater increase in engagement and dyad communication by 8 weeks that is sustained by 12 weeks (3 months).

It is further hypothesize that adolescents randomized to CloudConnect will have a lowering of HbA1c that is related to the increase in dyad disease-specific engagement. Moreover, our hypotheses are that this unique self-management approach in T1D will increase engagement of adolescents and their informal caregiver through increased communication and self-management behavior, and that this increase in engagement will lead to improved medical outcomes.

These hypotheses are based on data from preliminary studies collected by the study group and the literature. This preliminary data support that parents of adolescents with T1D are eager to follow their child's blood

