glucose tracing via remote monitoring — suggesting potential for an increase in involvement with such access and increase in disease-related communication. It is well described that an increase in parental involvement in diabetes control is associated with better medical outcomes such as lower HbA1c. Similarly, when adolescents exhibit increased degrees of participation in their care (such as a subset of adolescents who regularly used their CGM in a large-scale trial), this is associated with a lowering of HbA1c.

We will test these hypotheses using a randomized trial of CGM/Fitbit with no weekly feedback vs. CGM/Fitbit to CloudConnect. In addition to being compared against each other, both approaches will be compared to degree of engagement and efficacy of diabetes control experienced prior to the intervention, this information will be obtained at baseline. This randomized trial of CloudConnect in a chronic disease setting has been designed to assess changes in personal and dyad engagement and the relationship between this engagement and an important disease outcome.

Study Design: Biomedical

1. Will controls be used?

Yes

► IF YES, explain the kind of controls to be used.

The Control Group adolescent subjects will have the same inclusion/exclusion criteria and same characteristics as the Experimental Group adolescent subjects. The Control Group participants will use the study CGM, but subjects may elect not to set alarms or use the CGM Apps. This group will also use a study activity tracker (i.e Fitbit). Control subjects will use their personal insulin parameters throughout the trial. Control Group participants will use study insulin pen at mealtime with their home insulin. Control Group subjects will download their study equipment and provide it to the study team each week. The Control Group will **not** receive a weekly CloudConnect Report from the study team. Follow up visit in-clinic and phone calls, text messages and or/email will be the same as the Experimental Group.

2. What is the study design?

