another, this will be used as a variable in the comparison of mean glucose by CGM to evaluate whether there remained a difference in mean glucose once total daily steps was taken into account. Similarly, if there is an imbalance of key participant characteristics among participants who complete the study in one treatment group (such as higher proportion of multiple-daily-injection participants in the CloudConnect group), this will be considered as a variable in the multivariable ANOVA comparing mean glucose by CGM, as a secondary analysis.

5. What is your plan for secondary variable analysis?

- HbA1c
- Mean glucose by CGM
- Percent time in range 70-180 mg/dL
- Percent time in range 70-150 mg/dL
- Percent time <70 mg/dL
- Percent time >180 mg/dL
- Number of low BG
- Average daily insulin dose
- Average grams of carbohydrate entered
- Steps/day by Fitbit
- Questionnaires: Family Conflict Scale, Division of Diabetes Responsibilities, Child Self Management and My-Q scores.
- Response to weekly standardized questions:
 - i. *During the past week, did you talk with your parents about your diabetes management?*
(Yes=1, No=2)
 - ii. If you answered “yes,” how good or bad was the tone of that conversation?
(Likert scale: Very good = 1; good =2; Neutral = 3 bad =4; Very bad =5)
 - iii. During the past week, did you change your insulin parameters?
(Yes=1, No=2)

6. Have you been working with a statistician in designing this protocol?

No

7. Will data from multiple sites be combined during analysis?

No

Study Procedures-Biomedical Research

1. What will be done in this protocol?

PILOT STUDY:

Up to six adolescent subjects and six parent(s)/guardian(s) will be enrolled in a Pilot Study to assess the components used by the Experimental Group of the Main Study. This trial will evaluate if: (i) subjects can be trained to use study CGM + study Fitbit + personal pump (if pump user) or study insulin pen for mealtime

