 - On a scale of 1-7, with 1 being not at all useful and 7 being very useful, how useful were the weekly reports in helping you communicate with your parents/child about managing your/your child's diabetes? Can you tell me why you gave the score you did? What could have made the weekly reports more useful to you?
 - Is there anything else you would like to tell us about your experience with the weekly reports?

The weekly contact by phone, email or text for both the Control and Experimental Groups will be to:

- Check for AE or SAE
- Remind to download all the data (i.e. CGM, insulin pump/insulin pen, Fitbit data)
- Ask standardized questions, which will include the following:
 - For the child participant:
 - During the past week, did you talk with your parents about your diabetes management?
Yes or No
 - If you answered "yes," how good or bad was the tone of that conversation?
(Likert scale: Very good good Neutral bad Very bad)
 - During the past week, did you change your insulin parameters?
(Yes=1, No=2)
 - For the adult participant:
 - During the past week, did you talk with your child about his/her diabetes management?
Yes or No
 - If you answered "yes," how good or bad was the tone of that conversation?
(Likert scale: Very good good Neutral bad Very bad)
 - During the past week, did your child change his/her insulin parameters?
(Yes=1, No=2)

(Yes=1, No=2)

Visit 1: Adolescent subjects will be screened as indicated in the inclusion/exclusion criteria, and the consent form will be signed electronically after all the question related to the study are answered. The consenting process may occur over the phone/video or in-person. Demographic information and medical history information will then be obtained. A physical exam can either be performed at Visit 1 or documentation of a physical exam at a physician/provider visit within one year will suffice. Hemoglobin A1c will be collected with point-of-care equipment or at a local laboratory. This can be omitted if it is not possible to go to a laboratory or come to the clinic because of governmental restrictions such as Stay-at-Home orders. A urine pregnancy test will be required for adolescent girls who are able to become pregnant. Test must be negative to participate in the study.

If the adolescent subject meets eligibility, visit 1 and 2 may be combined. A repeat Hemoglobin A1c will be collected if visit 1 and 2 are greater than 28 days.

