Visit 2 (may be combined with Visit 1, may be done via phone or video): Adolescent subjects will be randomized and trained on the use of the study CGM and Fitbit. The CGM will be inserted into their abdomen per manufacturer instructions. Both Control and Experimental Group subjects will use their own personal pump. If the subject uses multiple daily injections (MDI), a commercially available Bluetooth connected insulin pen (inPen) will be given to both the Control and Experimental subjects in order to be able to collect the data accurately about meal time bolus treatments. Both pump users and MDI subjects will use their personal insulin. Each group will provide the study team weekly downloads from the study equipment and the personal insulin pump. Weekly CloudConnect reports will be provided to the Experimental Group participants *only*.

Depending on the subjects/family preference, the study team contact subjects via phone calls, text messages and/or emails at least once a week during the trial to:

- a) Remind them to download and transmit the data
- b) Check for AEs or SAEs
- c) Ask weekly standardized questions

All subjects will be reminded on how to download study data, if necessary. Both groups may complete a 1-week run-in period if they are CGM-naïve to ensure they are comfortable with the use of the study equipment, that all the study devices work properly, and to address issues related to transmission of the data to the study team. This run-in period may be repeated as necessary up to 3 times at the request of the study subject or study team. This data will not be included as part of the 12 week data collection. For subjects who have CGM experience, the investigator will determine if it is appropriate for he or she to skip the run-in period.

Visit 3 Check-in (Week 8 / on-site, email, or phone):

Subjects will download diabetes equipment weekly and submit the data to the study team for 12 weeks. Subjects may be asked to repeat a week of data collection if the quality of the data is insufficient for analysis.

A Check-In with the adolescent and parent/guardian will be completed to evaluate compliance and to answer any questions that the adolescent or parent may have about the study.

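### The hypothesised course of engagement (early rise, 8-week gain, return or maintenance at 12 weeks) cannot be measured from baseline on any one self-report instrument, because the weekly questions start only after randomisation

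*Combined protocol and SAP*

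**What the plan says.** The Rationale paragraph under Objectives/Hypothesis names two "measures of engagement (patient self-management behavior (i.e. personal insulin parameters) and diabetes-related dyad communication". It expects a modest early rise in the control arm, from new access to CGM or from being studied, after which these measures "will return to baseline levels by the 12-week evaluation". For the CloudConnect arm it expects a "greater increase in engagement and dyad communication by 8 weeks that is sustained by 12 weeks (3 months". The section ends by stating that "both approaches will be compared to degree of engagement and efficacy of diabetes control experienced prior to the intervention", with that information collected at baseline.

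Two kinds of self-report are scheduled in the Main Study:

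- **Questionnaires.** The FCI (the primary outcome), Child Self-Management, Diabetes Care and Communication and several others are completed at Visit 1 and again at study end.
- **Weekly questions.** There are three: whether the dyad talked about diabetes management in the past week, the tone if they did, and whether insulin parameters were changed. Statistical Considerations, item 5, lists "Response to weekly standardized questions" among the secondary outcomes. In Study Procedures, "The weekly contact by phone, email or text for both the Control and Experimental Groups will be to" check for adverse events, prompt downloads and put these questions to adolescent and parent.

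The Visit 2 paragraph is where "Adolescent subjects will be randomized and trained on the use of the study CGM and Fitbit". It is also where the weekly contacts are introduced, one purpose being to "Ask weekly standardized questions". The weekly questions appear in neither the Visit 1 procedures nor the Visit 1 questionnaire list.

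**The concern.** The hypothesis describes a course over time measured from a starting level: up, then a difference between arms at 8 weeks, then back down or held at 12. To show it, one instrument has to be recorded before the intervention, around week 8 and around week 12. The schedule does not appear to provide one.

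The likely improvisation at the analysis stage would be to use the first weekly answer as the starting level. The trial is open-label, so by then the dyad knows its arm and is using the study equipment. That is also the period in which the protocol itself expects engagement to be raised. A reference taken there would sit near the expected peak and would make an ordinary settling-down look like a fall below baseline. An answer not collected before randomisation cannot be recovered later.

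**Working it through.** **The plan's own figure.** The only calculation in the plan concerns the FCI (Statistical Considerations, item 2): mean 90.3, SD 12.5, difference 8.5%, power 80%, alpha 0.05 (taken as two-sided). The difference is 0.085 × 90.3 = 7.68 points. Then n per arm = 2 × (1.960 + 0.842)² × 12.5² / 7.68² = 42, close to the stated 40; power at 40 per arm is about 78%. This rests on a between-arm test of a questionnaire that has a Visit 1 value, so nothing below changes it.

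**Tracing the schedule.**

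| Self-report measure | Visit 1 | Around week 8 | About week 12 |
|---|---|---|---|
| FCI and other questionnaires | Yes | No | Yes |
| Weekly questions | No | Yes | Yes |

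1. *Visit 1.* The procedures are consent, history, physical exam, HbA1c and pregnancy test, plus the questionnaires. The three weekly questions are absent.
2. *Run-in.* It does not supply the missing value. It is described under Visit 2 after randomisation, experienced CGM users may skip it, and its data are kept out of the 12 weeks.
3. *Week 8.* The Visit 3 check-in covers compliance and participants' questions. No questionnaire is scheduled.
4. *Device data.* Downloads are also weekly, but they too are described from Visit 2 onward, and the note to the design figure treats what they yield as health outcomes.

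No row of the table is complete. The questionnaires allow a before-after contrast at about week 12. The weekly questions allow arms to be compared over time after randomisation. Neither allows the predicted 8-week increase to be measured from baseline.

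**What a first-week reference would do.** Let r be the initial rise above the usual level. Change measured from week 1 equals true change minus r, so the error equals the rise. Assume, purely for illustration, that 60% of dyads talk in a usual week, 80% in week 1 and 60% at week 12. Measured from week 1, the change is 60 − 80 = −20 points; measured from the usual level it is 60 − 60 = 0. With no initial rise the error is zero. The documents give no figure for r.

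**Value of a Visit 1 answer as a covariate.** If it correlated ρ with the on-study average, the residual variance would be multiplied by 1 − ρ²: 0.75 at ρ = 0.5 and 0.51 at ρ = 0.7, a cut of 25% to 49%. These correlations are assumed, and the formula is only approximate for yes/no answers. It should not be applied to the insulin-parameter item. Entry requires one month of stable insulin parameters (Inclusion/Exclusion Criteria, item 1), so nearly every Visit 1 answer would be No, and a near-constant covariate explains almost nothing.

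**The case against.** The best reply is that the hypothesis speaks of engagement and does not name the weekly questions. Statistical Considerations, item 2, says response will be assessed with the FCI, where higher scores mean more engagement and more diabetes-specific communication. The FCI and the rest of the battery are given at Visit 1 and at study end, so the promised comparison with pre-intervention engagement is met. The planned analysis of secondary outcomes is a between-arm t-test (item 4), which needs no baseline, and nothing in the plan proposes week 1 as a reference. Devices are not new to every dyad. The item content of most questionnaires is not given and the design figure is not shown, so some overlap with the weekly questions cannot be ruled out.

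Most of this stands, and it rules out several stronger readings. A reader might infer that engagement has no baseline at all, or that return to baseline at week 12 cannot be tested; the Visit 1 battery shows otherwise. A reader might infer that the between-arm comparison of the weekly items is compromised; randomisation protects it. A reader might take the 20-point error for a flaw in a planned analysis; no such analysis is planned, and the percentages are illustrative.

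What the reply does not answer is the 8-week part of the hypothesis. Whatever the questionnaires contain, they are not scheduled at week 8, and the one self-report that is available then has no pre-randomisation value.

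**Conclusion.** The point holds in a limited form. On the text of the visit schedule, all three weekly items lack a pre-randomisation value for adolescent and parent in every dyad, and every questionnaire lacks a week-8 value. The stated course of engagement therefore cannot be followed from baseline on any single self-report instrument. The primary comparison, the sample size and the between-arm tests of the weekly items are sound in this respect.

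This is a cheap improvement to a secondary outcome rather than a threat to the main result. The conclusion rests on the written procedures, since the design figure is unavailable. No precision gain should be quoted as established: the 25% to 49% range depends on assumed correlations, is measured against no adjustment at all although Visit 1 questionnaire scores could also serve as covariates, and fails for the insulin-parameter item.

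**What to change.** Ask the same three questions once at Visit 1, of the adolescent and the parent separately. State that they are completed before the arm is revealed, including when Visits 1 and 2 are combined. They should not simply be added to the questionnaire set, which may be answered remotely up to a week after the visit and so could fall after randomisation.

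Use the talked and tone answers as the baseline for the trajectory and, where available, as a covariate in the between-arm comparison of those items. Claim no variance gain for the insulin-parameter item. State that the first on-study week will not serve as the baseline.

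If the questions are not added, reword the hypothesis so that the return-to-baseline and 8-week change claims go no further than the Visit 1 instruments can show, which in practice means change at about week 12.

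The cost is about a minute per person. The limits are that one answer covers a single pre-study week, and that dyads who did not talk in that week will have no baseline for tone.

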This is a randomized control, open-label, single-site clinical trial. We will target completion by eighty adolescents (age 12-17 years) with Type 1 diabetes and their parent/guardian (age 18+) to participate in a 3 month outpatient study. Participants will be randomized to either a Control Group or Experimental Group. Both groups will use the study continuous glucose monitor, study activity tracker, and a study insulin pen if an multiple daily injection (MDI) user. Subjects who use an insulin pump to treat their type 1 diabetes will use their personal insulin pump. All subjects will be asked to download this equipment and provide it to the study team each week. The study team will communicate weekly with each group. Questionnaires will also be completed at the beginning and at the end of the study. The Experimental Group will receive the CloudConnect Reports. The Control Group will not receive this feedback.

3. Does the study involve a placebo?

No

Human Participants

Ages: 12-17 years old and at least one of parent(s)/guardian(s) (age 18+)/guardian (adolescent/parent dyad is required for participation in this trial)

Sex: Male and Female

Race: All

1. Provide target # of subjects (at all sites) needed to complete protocol.

For the Pilot Study, up to 6 adolescents and 6 parent(s)/guardian(s) may complete the study. These pilot subjects may also participate in the Main Study.

For the Main Study, 160 subjects (80 dyads – consisting of 80 adolescents and 80 adults) need to complete the study.

2. Describe expected rate of screen failure/ dropouts/withdrawals from all sites.

We expect that because the length of the study it could be 20-30% dropouts/withdrawals from the study.

3. How many subjects will be enrolled at all sites?

This is a single site clinical trial to be completed at UVa.

4. How many subjects will sign a consent form under this UVa protocol?

Up to 210 subjects (105 dyads – consisting of 105 adolescents and 105 parent(s)/guardian(s)) will sign consent for the Main Study and up to 16 subjects (8 parent/child dyads) will sign a consent for the Pilot Study. i.e. total = 226 (210+16)

Inclusion/Exclusion Criteria

1. List the criteria for inclusion for Pilot and Main Study Adolescent Subjects

- Willingness to provide informed consent
- Adolescents ages ≥ 12 and ≤ 17 years old with a parent/guardian (18+ yo) who is willing to participate with the child

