Study Objectives & Endpoint Definitions:

As mentioned previously, this project seeks to assess how CloudConnect affects participant engagement, dyad engagement, and clinical outcomes in adolescent T1D.

We will assess how adolescents and their parent(s)/guardian(s) respond to this new approach using the Family Communication Inventory (FCI). This diabetes-specific approach was designed by the investigators to assess parent-child communication regarding tasks (discussion of insulin dosing for a given meal, BG trends, need for dose changes). As an outcome measure, scores for parents and adolescents are summed, with higher scores representing higher degree of engagement and T1D-specific communication.

Power/Precision of the study to address major study endpoints:

In using the FCI, we determined based on preliminary data from 220 adolescent/parent participants eligible for the study, with mean (90.3) and standard deviation (12.5) that we are powered to detect a difference of 8.5% in this outcome in the treatment group with 80% power and an alpha of 0.05. This study will require 40 adolescent participants with 40 parent(s)/guardian(s) to complete per arm. Assuming a non-adherence/drop-out rate of 20-30% for Intention-to-Treat (ITT) analysis, 55 participants is yielded per arm.

3. Provide a justification for the sample size used in this protocol.

The study team will attempt to enroll an equal number subjects based on gender, CSII, and MDI use. The study is powered to detect a difference of 8.5% in this outcome in the treatment group with 80% power and an alpha of 0.05. This study will require 40 adolescent participants with 40 parent(s)/guardian(s) to complete per arm. Assuming a non-adherence/drop-out rate of 20-30% for Intention-to-Treat (ITT) analysis, 55 participants is yielded per arm.

4. What is your plan for primary variable analysis?

Because this is a randomized study, our primary outcome (score on the Family Communication Inventory) will be by t-test comparing those randomized to CloudConnect to usual care+CGM. Comparison of secondary outcomes between treatment groups will also be t-tests. Secondary analyses of both the primary and secondary outcomes will utilize multivariable ANOVA, particularly in the event that key variables differ between groups. For example, if average steps per day [as a measure of exercise] is higher in one group vs.

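### The hypothesis is a gain by week 8 that is sustained at week 12, but no planned analysis distinguishes week 8 from week 12, although weekly data that could do so are collected

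*Combined protocol and SAP*

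**What the plan says.** - **Hypothesis (Objectives/Hypothesis, Rationale).** Controls are expected to improve a little at first, after which "their measures of engagement (patient self-management behavior (i.e. personal insulin parameters) and diabetes-related dyad communication") should fall back to baseline by week 12. The CloudConnect arm, by contrast, "will have a greater increase in engagement and dyad communication by 8 weeks that is sustained by 12 weeks (3 months").
- **Commitment to test (same section).** "We will test these hypotheses using a randomized trial". In addition, "both approaches will be compared to degree of engagement and efficacy of diabetes control experienced prior to the intervention".
- **FCI schedule.** Under Study Design: "Questionnaires will also be completed at the beginning and at the end of the study". The Main Study procedures agree: the questionnaires follow Visit 1 and are repeated at the end of participation. The week-8 visit (Visit 3, and Subject Compliance) covers compliance and participants' questions; no questionnaire is listed. Figure 1 is not shown in the available copy, but the text is explicit.
- **Weekly data (Main Study procedures).** In both arms, through all 12 weeks, adolescent and parent are asked separately whether they talked about diabetes management, the tone if they did, and whether insulin parameters changed. These items are listed as secondary variables in Statistical Considerations, question 5, which prints only the adolescent wording.
- **Analysis (Statistical Considerations, question 4).** For the FCI, on which "scores for parents and adolescents are summed", "our primary outcome (score on the Family Communication Inventory) will be by t-test comparing those randomized to CloudConnect to usual care+CGM". The secondary variables, weekly items included, get the same treatment: "Comparison of secondary outcomes between treatment groups will also be t-tests". Multivariable ANOVA is added as a secondary analysis and described only as adjustment for variables that differ between groups.

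**The concern.** The hypothesis has two parts tied to time: a greater gain by week 8, and its persistence to week 12. A week-12 difference on the FCI would show that the CloudConnect arm is higher at week 12 and nothing about either part. A null result at week 12 could not be told apart, on the FCI, from an early gain that faded. For an intervention made of weekly reports, those two results lead to different design conclusions, and informing technology design is a stated aim of the project.

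The weekly items follow the course directly, but a t-test on a 12-week summary averages over it. The plan also does not say how up to 12 weekly answers from each of two respondents become one value. The choice of week or summary therefore stays open until the data are seen, in an open-label trial.

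**Working it through.** **1. What the sample size was built for.** Inputs from Statistical Considerations, question 2: mean 90.3, SD 12.5, difference 8.5%, power 80%, alpha 0.05 (two-sided assumed).

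- Difference: 0.085 × 90.3 = 7.68 points.
- n per arm = 2 × (1.960 + 0.842)² × (12.5/7.68)² = 41.6, so 42, against the stated 40. Power at 40 per arm is 0.784.

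The stated figure reproduces closely. It matches one two-group comparison at one time; no week-8 measurement and no correlation over time enters it.

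**2. Hypothesis against measurement and analysis.**

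| Part of the hypothesis | FCI | Weekly items |
|---|---|---|
| Greater gain by week 8 | No observation scheduled between start and end | Collected; only a between-group t-test planned |
| Sustained at week 12 | Week-12 level only; no week 8 to compare with | Collected; no contrast between periods planned |
| Controls return to baseline | Baseline and end measured; comparison intended, no method given | No pre-randomisation answers described |

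**3. What the weekly items could show.** Inputs: 40 dyads per arm (documents). Assumed, because the documents give neither: a proportion p answering yes of 0.5 to 0.9, and a within-person correlation ρ between weeks of 0.3 to 0.7. One respondent, 95% half-width in percentage points:

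half-width = 100 × 1.96 × √(2 × p(1−p) × V / 40)

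V depends on the contrast and on how correlation behaves over time.

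- *Single week*, V = 1: p = 0.5 gives 21.9; p = 0.9 gives 13.1.
- *Weeks 5-8 mean, equal correlation between all weeks*, V = (1 + 3ρ)/4: p = 0.5 gives 15.1 (ρ = 0.3) to 19.3 (ρ = 0.7); p = 0.9 gives 9.1 to 11.6.
- *Change from weeks 5-8 to weeks 9-12, equal correlation*, V = (1 − ρ)/2: p = 0.5 gives 13.0 (ρ = 0.3) to 8.5 (ρ = 0.7); p = 0.9 gives 7.8 to 5.1.
- *Same change, correlation decaying by week* (AR(1), lag-one ρ = 0.3, 0.5, 0.7), V = 0.701, 0.812, 0.794: p = 0.5 gives 18.4, 19.7, 19.5; p = 0.9 gives 11.0, 11.8, 11.7.

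The change between periods therefore has a half-width of about 5 to 20 points. Under equal correlation a higher ρ narrows it; under decay it does not. A second respondent should narrow it somewhat, by an amount that depends on parent-adolescent agreement, which the documents do not give.

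**4. Would an FCI at week 8 settle it?** Taking 12.5 as the SD of the summed score and an assumed week-8 to week-12 correlation of 0.5 to 0.8, the between-arm change has half-width 1.991 × 12.5 × √(2(1 − ρ)) × √(2/40) = 5.56 to 3.52 points. That is 72% to 46% of the planned 7.68. Even with no observed change, a loss of about half or more of the planned difference could mostly not be excluded.

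**The case against.** The strongest reply is that the primary question is the week-12 FCI comparison, which is measured, powered and analysed consistently. The time course could then be read as motivation. The first half is right. The second is not, because the time course is worded as the study's hypothesis and followed by a statement that it will be tested.

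Four further points stand and limit the concern.

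- A reader might infer that the plan contains no comparison over time at all. It does not go that far: both arms are to be compared with their state before the intervention. The statistical section gives no method for this, and it cannot separate week 8 from week 12, but it is an intended comparison over time.
- A reader might want to use insulin dose, carbohydrate entered and steps as further tests of engagement. The documents do not support that. The Main Study procedures class them as secondary health outcomes, question 4 treats steps as a measure of exercise, and the Rationale ties self-management behaviour to insulin parameters.
- A reader might conclude that the FCI must be added at week 8. On the figures above it could not by itself establish persistence, and it might prompt communication before the primary endpoint. It is not recommended.
- The weekly items are an imperfect substitute. A yes/no answer on whether the pair talked covers much less than the FCI, and the precision is modest.

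**Conclusion.** The point holds as a gap between hypothesis and analysis. A gain by week 8 that is sustained at week 12 is hypothesised, and nothing planned distinguishes those two times. The documented facts are: no FCI observation scheduled in the text between start and end; up to 12 weekly answers per item from each of two respondents per dyad; and a between-group t-test as the only stated comparison for them. For the FCI the limit lies in the schedule; for the weekly items it lies only in the analysis plan.

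It would be a mistake to read this as a flaw in the primary analysis: the week-12 comparison and its sample size are unaffected. The 5 to 20 point range is an illustration resting on assumed proportions, correlations and correlation structure. It shows that the weekly items can describe the course but may not exclude a sizeable fade. This is a cheap improvement that should be made, not a threat to the trial.

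**What to change.** Add a paragraph to Statistical Considerations, questions 4 and 5:

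1. Analyse the two weekly yes/no items (talked; insulin parameters changed) from both respondents with a GEE or mixed model with arm-by-week terms, clustered by dyad.
2. Because one week is imprecise, report the arm contrast for weeks 5-8, for weeks 9-12, and the change between them, each with a 95% confidence interval. State how weeks are numbered when a data week is repeated, which the procedures allow.
3. Report tone descriptively among those who talked, since it is asked only after a yes.
4. Limit FCI conclusions to week 12, and tie the week-8 and persistence claims to the weekly items. Treat the change as descriptive unless a margin for what counts as sustained is set in advance.
5. Device measures may be modelled over time as health outcomes, not as tests of the engagement hypothesis.

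The cost is drafting and analysis time; data collection, sample size and the primary test do not change. Two limits remain. With no described pre-randomisation answers, the weekly items give arm contrasts over time, so the predicted return of controls to baseline stays untested on them. They also cover less than the FCI.
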